15.1. Prohibited Medications

Subjects may not use medications listed below within the time periods indicated and may not use the following drugs during the study:

- HMG Co-A reductase inhibitor (statin) concurrently or within 30 days prior to randomization (Visit T1);
- cyclosporine, cholestyramine, probenecid, fibrate drugs, or medications contraindicated during lactation concurrently or within 30 days prior to randomization (Visit T1);
- experimental or investigational drugs concurrently or within 30 days or 5 half-lives of the drug, whichever is longer, prior to screening (Visit S1);
- concomitant use or use within 30 days prior to randomization (Visit T1) of drugs that decrease breast milk production, such as pseudoephedrine; or
- concomitant use or use within 30 days prior to randomization (Visit T1) of drugs that increase breast milk production, such as domperidone.

16. STUDY MEDICATION EXPOSURE AND TREATMENT COMPLIANCE

Study drug exposure duration (days) will be summarized by cohort on FAS.

In addition, estimated compliance with study drug will be presented for the FAS by cohort. The subjects will be grouped as compliant, i.e., those who have 100% of required tablets while on treatment versus non-compliant (<100% compliance).

Per protocol, subjects will take 1 tablet of the study drug once daily, starting from the visit day at which their study drug is initially dispensed (date of Visit T1) to the day of last dose on Day 6. The percentage of compliance will be based on drug accountability data and calculated by the formula using counts of tablets:

Total tablets taken = [tablets dispensed - tablets returned on Day 5] + 1 (if the last dose on Day 6 is administered)

% Compliance = [Total tablets taken] *100 / [treatment duration (days)],
where the protocol-defined treatment duration is 6 days.

The percentage compliance is capped as a maximum of 100% if it exceeds 100%.

Note that subjects who did not receive any study drug or did not report any drug accountability data will be counted as noncompliant (0%).

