## **8. TREATMENT OF SUBJECTS**

### **8.1 Administration of Investigational Medicinal Product**

On Day 1 (Visit T1) of the Treatment Period, subjects will be randomized to receive bempedoic acid (Cohort 1) or bempedoic acid/ezetimibe FCDP (Cohort 2). Each dose of IMP is comprised of 1 tablet from a bottle. The CRU staff will administer IMP to subjects in the unit on Day 1 and Day 6 of the study. The IMP will be self-administered by subjects on Day 2 through Day 5 at home. Subjects will be instructed to take IMP once daily at approximately the same time each morning ( $\pm$  2 hours) with or without food. On the evening of Day 5 (Visit T2), subjects will check-in to the CRU and CRU staff will administer IMP on the morning of Day 6.

Study staff will call subjects on Days 2 through Day 5 to ensure they are taking IMP appropriately. Day and time of IMP administration must be captured in the Study Drug Diary. If the subject forgets to take IMP at the same time ( $\pm$  2 hours) Day 2 through Day 5, it may be taken up to 6 hours later the same day. After that, the subject should not take IMP that day and the Sponsor should be contacted to determine if the subject should continue or be replaced in the study. The details describing the reason for the missed dose should be documented in the subject's medical record. Extra IMP is provided and can be used to replace a dose of IMP that cannot be used if lost or damaged.

Other details regarding IMP including description, supply and control, accountability, handling, and disposal are provided in [Section 0](#).

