### **10.3.2 Treatment Day 1 (Visit T1)**

Subjects who continue to meet all inclusion criteria and none of the exclusion criteria may be randomized into the study. Each subject will undergo the following assessments:

- Review of current breastfeeding practices per subject report, including:
  - frequency and duration of feeds for infants fed from the breast,
  - bottles/day and ounces/day for infant's fed pumped breast milk from a bottle, and
  - use of formula supplementation (bottles/day, ounces/day and duration of supplementation);
- confirm subject is maintaining adequate breast milk production (document duration of weaning, if applicable) per subject report;
- confirm infant is able to bottle feed prior to randomization (Visit T1) per subject report;
- confirm adequate breast milk/infant formula is available to feed the infant after first dose of IMP (Visit T1) through Day 13 (Visit FU1) per subject report;
- adverse event review;
- concomitant medicine review;
- weight;

- vital signs;
- urine pregnancy test;
- predose breast milk collection ( $\leq$ 1 hour before IMP administration);
- predose blood sample for chemistry and hematology;
- predose blood sample for plasma PK;
- administer first dose of IMP;
- dispense IMP for self-administration on Day 2 through Day 5;
- provide Study Drug Diary; and
- schedule optional lactation consultant visit.

The IMP will be administered by study staff only after the predose breast milk collection, predose chemistry and hematology, and predose plasma PK sample are collected. Subjects must be reminded to not feed their infant breast milk produced after the first dose of IMP through Day 13 of the study.

Subjects will be instructed to take IMP at the same time ( $\pm$  2 hours) every day with or without food for Day 2 though Day 5 and to complete the Study Drug Diary.

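### The SAP section 16 compliance formula can misstate doses taken: missing accountability is scored 0%, lost tablets count as taken, and the place of the Day 1 tablet is undefined

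*SAP*

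**What the plan says.** SAP section 16 presents compliance by cohort on the Full Analysis Set (FAS). The numerator is "Total tablets taken = [tablets dispensed - tablets returned on Day 5] + 1 (if the last dose on Day 6 is administered"). The denominator is the treatment duration, "where the protocol-defined treatment duration is 6 days", and the percentage is capped at 100. Women are then split into two groups: "those who have 100% of required tablets while on treatment versus non-compliant (<100% compliance"). A closing note says that subjects who received no study drug or "did not report any drug accountability data will be counted as noncompliant (0"%).

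The protocol describes how doses reach the women. Under section 8.1, staff give the Day 1 and Day 6 doses in the unit and the women take Days 2 to 5 at home. Section 10.3.2 lists the first dose as one step and, as a separate step after it, "dispense IMP for self-administration on Day 2 through Day 5". Section 8.1 also provides for spares: "Extra IMP is provided and can be used to replace a dose of IMP that cannot be used if lost or damaged". Section 9.5 asks for unused product back at check-in and has the site log tablets that were lost or broken.

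The tablet count is not the only dose record. Section 8.1 states: "Day and time of IMP administration must be captured in the Study Drug Diary". Section 9.4 has staff judge adherence from phone calls, the diary and the count of returned tablets together.

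**The concern.** The SAP uses one of the three adherence sources that the protocol collects, and its rules conflict with known facts in foreseeable cases.

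- **Missing accountability.** The 0% rule treats an absent form as proof that nothing was taken. SAP section 6.1 admits a woman to the FAS only if she received at least one dose, so within that set the score is false.
- **Lost tablets.** A tablet that is neither swallowed nor returned is counted as taken. The protocol expects such losses, supplies spares and logs them, but the formula has no term for them.
- **Day 1 tablet.** The formula adds back the staff-given Day 6 dose and has no matching term for the staff-given Day 1 dose. That is right only if the Day 1 tablet is inside the dispensed count, and the SAP does not say so.

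At stake is the accuracy of one reported table. Because the cut-off is exactly 100%, an error of a single tablet moves a woman between the two groups, and each cohort has only 8 evaluable women.

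**Working it through.** **Inputs.** Six doses: Days 1 and 6 given by staff, Days 2 to 5 at home (protocol 8.1). Bottle of 30 tablets (protocol 9.3), used for illustration; only dispensed minus returned matters. Denominator 6, cap 100%, missing accountability 0% (SAP 16). FAS requires at least one dose (SAP 6.1). Whether the Day 1 tablet is in the dispensed count is not stated, so both cases are shown.

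**Formula.** With D dispensed, R returned and the Day 6 dose given, score = min(100, 100 × (D − R + 1)/6).

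**Full adherence, nothing lost.** The plan's target is 6 of 6.
- Day 1 tablet in the count: D = 30, R = 25, so (30 − 25 + 1)/6 = 6/6 = 100%. The target is reproduced.
- Day 1 tablet not in the count: D = 29, R = 25, so (29 − 25 + 1)/6 = 5/6 = 83.3%. She is classed as non-compliant.

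**Lost tablets.** Let M be missed home doses and L tablets lost and not returned. The true value is (6 − M)/6. The formula gives (6 − M + L)/6 with Day 1 in the count and (5 − M + L)/6 with it out, each before the cap.

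| M | L | True | Day 1 in count | Day 1 not in count |
|---|---|---|---|---|
| 1 | 0 | 83.3% | 83.3% | 66.7% |
| 0 | 1 | 100% | 116.7%, capped to 100% | 100% |
| 1 | 1 | 83.3% | 100% | 83.3% |
| 1 | 2 | 83.3% | 116.7%, capped to 100% | 100% |
| 2 | 2 | 66.7% | 100% | 83.3% |

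Before the cap, the error is +L tablets if Day 1 is in the count and L − 1 tablets if it is not. With one lost tablet the second case is therefore right by accident, because the lost tablet cancels the omitted Day 1 dose.

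**Missing accountability.** The rule gives 0%. Staff-given doses alone give 1/6 = 16.7% (Day 1 only) or 2/6 = 33.3% (Days 1 and 6). If the diary documents Days 2 to 5, the figure is 6/6 = 100%. One such woman among 8 fully adherent women lowers her cohort's compliant proportion from 8/8 = 100% to 7/8 = 87.5%.

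**The case against.** The strongest reply is that these are rare cases in a small, closely watched study. A wrong compliant label from a lost tablet needs a missed dose and an unreturned tablet in the same woman within four home days. Damaged tablets should normally come back with the unused product. Sites must keep dispensing and return logs, so having no accountability data would itself be a departure from the protocol, and the 0% rule can only make adherence look worse. SAP section 16 also dates initial dispensing to Visit T1, which suggests that the Day 1 tablet is in the count; the added 1 is then needed only because product is returned before the Day 6 dose. All of this stands and limits the size of the point. It does not make the stated rules correct when those cases arise.

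A reader might infer more than the documents support:

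- **That the formula simply omits the Day 1 dose.** The SAP leaves the term undefined, so this error is conditional. It also cannot be combined with the example of one missed dose and one lost tablet, which is wrong only when Day 1 is in the count.
- **That the on-treatment wording contradicts the fixed denominator.** The SAP sets the duration at 6 days explicitly. A woman who stops after Day 3 scores 3/6 = 50% under the plan and also under the fix below. The wording is loose, but no error in the calculation follows.
- **That this table is the only place where missed doses would show.** Deviations are listed and important ones summarized (SAP 10), missed doses go to the Sponsor at once (protocol 9.4), and a woman who does not receive six doses is to be replaced (protocol 6.7).
- **That primary results are affected.** Compliance does not define the PK Analysis Set (SAP 6.2) and does not enter daily infant dosage or RID (SAP 17.3). A missed dose would lower milk concentrations, but the label in this table does not alter them.

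**Conclusion.** The concern holds as a minor one. The 0% rule is wrong for any FAS member it touches, under every reading: the true figure is at least 16.7%, at least 33.3% if Day 6 was given, and possibly 100%. Counting lost tablets as taken overstates compliance by one tablet in the case of one missed dose and one lost tablet (100% against 83.3%), provided that the Day 1 tablet is in the dispensed count. If it is not, that case comes out right and the fault moves to the fully adherent woman with no lost tablets, who scores 83.3%. The documents do not settle which convention applies, nor how often tablets or forms will be lost, so the number of women affected cannot be estimated. The consequence is confined to a descriptive table.

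**What to change.** Define compliance in SAP section 16 from dose records:

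100 × (staff-recorded Day 1 dose + diary-recorded doses on Days 2 to 5 + staff-recorded Day 6 dose) / 6

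This gives 6/6 = 100% for full adherence under either dispensing convention, and 5/6 = 83.3% for one missed home dose whether or not a tablet is lost.

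Keep the tablet count as a cross-check. State whether the Day 1 tablet is in the dispensed count and, if it is not, add 1 for it. Subtract lost or damaged tablets that were not returned. Allow for returns on the morning of Day 6, which the schedule of events permits with Sponsor approval. Delete the rule that scores missing accountability data as 0%.

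The cost is SAP wording. The diary, tablet counts and loss log are already collected. The SAP already relies on the Day 1 dosing date for its reference date and on whether the Day 6 dose was given for its present formula. The downside is small: home doses would rest on the women's own diary entries, which the tablet count and the daily calls on Days 2 to 5 can check.

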17. PHARMACOKINETIC (PK) ANALYSIS

17.1. PK Nominal Timepoints

Table 1 Schedule of Dosing and Sample Collection

Time	Day 1	Day 2	Day 3	Day 4	Day 5	Day 6	Day 7
Dosing (once per day)	X	X	X	X	X	X	
Sample	Plasma, Milk					Milk*	Plasma, Milk*

*On Days 6-7, breast milk will be collected during the intervals of 0-3h, 3-6h, 6-9h, 9-12h, 12-16h, 16-20h, and 20-24h after Day 6 dose administration

PK milk samples will be collected at the following nominal timepoints –

- Visit T1 (Day 1) Pre-dose (\leq 1 hour before IMP administration)
- Visit T2 (Day 6 and 7) at 3, 6, 9, 12, 16, 20 and 24 hours (\pm 30 minutes) after Day 6 dose administration.

PK plasma samples will be collected at the following nominal timepoints –

- Visit T1 (Day 1) Pre-dose (\leq 1 hour before IMP administration)
- Visit T2 (Day 7) at 24 hours (\pm 30 minutes) after Day 6 dose administration.

17.2. PK Parameters

The PK parameters listed in the table below are estimated for this study, and used for the primary and the secondary endpoints estimate:

Table 2 PK Parameters

Cohort [IMP]	Specimen	Analytes	PK Parameter
Cohort 1 [BA]	Milk	ETC-1002, ESP15228, ETC-1002-glucuronide	C_{max} , T_{max} , C_{trough} , AUC_{24h} , C_{avg}
	Plasma	ETC-1002, ESP15228, ETC-1002-glucuronide	C_{trough} , M/P ratio*
Cohort 2 [BA/EZE FCDP]	Milk	ETC-1002, ESP15228, ETC-1002-glucuronide, EZE, EZE-glucuronide	C_{max} , T_{max} , C_{trough} , AUC_{24h} , C_{avg}
	Plasma	ETC-1002, ESP15228, ETC-1002-glucuronide EZE, EZE-glucuronide	C_{trough} , M/P ratio*

* M/P ratio = C_{trough} (Milk)/ C_{trough} (Plasma) at 24 hours after Day 6 dose administration.

17.3. PK Analysis for Primary Endpoints

The 1st primary endpoint - **daily infant dosage** (mg/day) of BA or EZE will be calculated as the amount of drug in breast milk collected over 24 hours (starting on Day 6 post study treatment) for individual subjects, where the amount of drug in breast milk is calculated as the sum of total drug concentration in each milk collection multiplied by the expressed milk volume in each milk collection.

Daily infant dosage (Dose_{ij}) = $\Sigma (C_{ij} \times V_{ij})$, where

Dose_{ij} = daily infant dose based on collected drug concentration in breast milk and expressed breast milk volume

C_{ij} = drug concentration in breast milk from each collection

V_{ij} = breast milk volume collected at each nominal timepoint

i = nominal timepoints within 24 hours post study treatment on Day 6

j = subjects (8 in each cohort, 16 in total)

- The 2nd primary endpoint - **relative infant dose (RID)** of BA (for Cohort 1 and 2 respectively) or EZE (for Cohort 2 only) equals the percent of the weight-adjusted maternal dosage consumed by infant via breast milk over 24 hours.

RID (%) = Estimated daily infant dosage (mg/day/kg) / Maternal dosage (mg/day/kg) x 100.

The estimated daily infant dosage will be calculated as the average drug concentration in breast milk over 24 hours after the Day 6 dose administration (C_{avg}) multiplied by 150 mL/day/kg, the estimated standard infant milk intake over 24 hours. Maternal dosage will be calculated as the mean maternal dosage (mg/day per kg baseline body weight determined on Day 1).

Estimated daily infant dosage (mg/day/kg) = C_{avg} (mg/ml) x 150 (ml/day/kg)

Maternal dosage (mg/day/kg) = daily dose of study treatment (mg/day) / baseline body weight (kg)

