**Pharmacokinetic Assessments**

**Primary Endpoints**

Bempedoic acid and ezetimibe assessments:

- Daily infant dosage calculated as the cumulative amount excreted in breast milk per day
- RID calculated as the ratio of total infant daily dose per kg of body weight and maternal daily dose per kg of body weight multiplied by 100

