**Statistical Methods:**

A minimum sample size of 16 (8 bempedoic acid [Cohort 1] and 8 bempedoic acid/ezetimibe FCDP [Cohort 2]) evaluable subjects (who complete the 6-day treatment period and 24-hour breast milk collection) is planned for this study. The sample size was determined to be sufficient to address the objectives of the study. Sample size was not based on empirical or hypothesis testing criteria

Breast milk PK endpoints of daily infant dosage, RID, amount excreted, AUC and peak, trough and average concentrations will be summarized using descriptive statistics for bempedoic acid, ESP15228, bempedoic acid glucuronide, ezetimibe and ezetimibe glucuronide. Plasma trough concentrations of bempedoic acid, ESP15228, bempedoic acid glucuronide, ezetimibe and ezetimibe glucuronide will be summarized using descriptive statistics.

For all enrolled subjects who receive at least 1 dose of IMP (safety population), safety data (including adverse events, clinical laboratory parameters, physical examination, vital signs and body weight) will be summarized and listed using descriptive statistics.

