### 5.2 Endpoints

#### 5.2.1 Pharmacokinetic Assessments

##### 5.2.1.1 Primary Endpoints

Bempedoic acid and ezetimibe assessments include:

- daily infant dosage calculated as the cumulative amount excreted in breast milk per day, and
- RID calculated as the ratio of total infant daily dose per kg body weight and maternal daily dose per kg of body weight multiplied by 100.

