#### 14.3.2.1 Primary Analyses

- Daily infant dosage and RID of bempedoic acid will be summarized for Cohort 1 subjects who receive once daily bempedoic acid for 6 consecutive days.
- Daily infant dosage and RID of bempedoic acid and ezetimibe will be summarized for Cohort 2 subjects who received once daily bempedoic acid/ezetimibe FCDP for 6 consecutive days.
- RID will be calculated as the ratio of total infant dose per kg body weight and maternal dose per kg body weight, multiplied by 100.

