2. STUDY OBJECTIVES

2.1. Primary Objective

The primary objectives of this study are to estimate infant exposure to bempedoic acid (BA) or bempedoic acid and ezetimibe (BA+EZE):

- estimate the daily infant dosage and relative infant dose (RID) of BA in mature breast milk after administration of BA for 6 consecutive days (Cohort 1).
- estimate the daily infant dosage and RID of BA and EZE in mature breast milk after administration of bempedoic acid/ezetimibe fixed combination drug product (FCDP) for 6 consecutive days (Cohort 2).

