2.2. Secondary Objective(s)

The secondary objectives of this study are to characterize the excretion of BA or BA+EZE in mature breast milk of healthy lactating women who receive a once daily dose of BA or FCDP for 6 consecutive days:

- determine concentrations of BA (ETC-1002), active metabolite (ESP15228) and inactive metabolite (ETC-1002-glucuronide) in mature breast milk collected over 24 hours from healthy subjects administered BA (Cohort 1) or FCDP (Cohort 2),
- determine concentrations of EZE and active metabolite ezetimibe-glucuronide (EZE-glucuronide) in mature breast milk collected over 24 hours from healthy subjects administered FCDP (Cohort 2).

2.3. Safety:

The safety objective of this study is to evaluate the safety of 6 consecutive doses of BA or FCDP in healthy lactating women.

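### Does the plan leave out a daily infant dose for the active metabolites that the protocol synopsis appears to promise?

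*SAP*

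**What the plan says.** The synopsis of the protocol, under Statistical Methods, lists the milk endpoints together: "Breast milk PK endpoints of daily infant dosage, RID, amount excreted, AUC and peak, trough and average concentrations will be summarized using descriptive statistics for" five analytes. The end of that sentence names them: "average concentrations will be summarized using descriptive statistics for bempedoic acid, ESP15228, bempedoic acid glucuronide, ezetimibe and ezetimibe glucuronide".

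Every other place that sets the scope of daily infant dosage and RID is narrower:

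- Protocol synopsis, Primary Endpoints: "Bempedoic acid and ezetimibe assessments".
- Protocol 5.2.1.1: "Bempedoic acid and ezetimibe assessments include".
- Protocol 14.3.2.1, for the combination cohort: "Daily infant dosage and RID of bempedoic acid and ezetimibe will be summarized for Cohort 2 subjects".
- SAP 2.1, for the same cohort: "estimate the daily infant dosage and RID of BA and EZE in mature breast milk".
- SAP 17.3 gives daily infant dosage in "mg/day) of BA or EZE will be calculated as the amount of drug in breast milk collected over 24 hours", and RID for BA in both cohorts and EZE in Cohort 2.

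Protocol 14.1 and SAP section 1 both let the SAP prevail on analysis.

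For the metabolites, SAP 2.2 sets the objective of determining concentrations, including "active metabolite (ESP15228) and inactive metabolite (ETC-1002-glucuronide) in mature breast milk collected over 24 hours". It also labels EZE-glucuronide active. SAP 3.2, Table 2 in SAP 17.2 and SAP 17.4 plan amount per collection, AUC24h, Cavg, Cmax, Tmax and Ctrough for them. The last list of summaries in SAP 17.4 (daily infant dosage, estimated daily infant dosage, RID, M/P ratio) names no analytes.

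**The concern.** One part of the protocol seems to promise infant dosage for metabolites, and the governing document does not deliver it. Two of the three metabolites are called active by the sponsor, and the study exists to inform decisions about infant exposure. A reader would see a 24-hour infant amount for BA and EZE but none for ESP15228 or EZE-glucuronide.

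The per-collection amounts are planned, but nothing says that the seven are added up for each woman. Amount per collection is also absent from Table 2 and from the parameters named for summary in SAP 17.4. If a metabolite total were wanted later, it would come in under the ad hoc provision of SAP 5.2, after the data had been seen.

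**Working it through.** **Which text states the plan.** Set side by side, the synopsis sentence on statistical methods is alone. The synopsis's own primary endpoints, protocol 5.2.1.1 and 14.3.2.1, and SAP 2.1 and 17.3 all limit the two measures to BA and EZE. The synopsis gives infant dosage and RID for two analytes under Primary Endpoints, and amount excreted, AUC and concentrations for five under Secondary Endpoints. The Statistical Methods sentence runs both lists together before a single list of analytes. That is a drafting slip, and the SAP dropped nothing that was consistently planned.

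**Whether the sentence could be carried out.** SAP 17.3 has

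RID (%) = [Cavg × 150 mL/kg/day] ÷ [daily dose of study treatment ÷ maternal baseline weight] × 100.

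The denominator is an administered dose. No metabolite is administered, so a metabolite RID needs a parent-equivalent conversion that neither document defines. The sentence cannot have been meant literally for all five analytes.

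**Whether an objective is missed.** Protocol 4.1 and 5.1.1 and SAP 2.1 tie infant exposure to BA, or to BA and EZE. The metabolite objective is about milk concentrations, and the planned parameters describe those fully.

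**What is absent, and what can be derived.** Inputs: the collection intervals in Table 1 of SAP 17.1, the 150 mL/kg/day in SAP 17.3, and 8 women per cohort.

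- Intervals: 3 + 3 + 3 + 3 + 4 + 4 + 4 = 24 h. The sum of the seven per-collection amounts is therefore exactly the Σ(C × V) that SAP 17.3 uses for the parents.
- Per-kg dose: 1 ng/mL × 150 mL/kg/day = 150 ng/kg/day = 0.15 µg/kg/day. A Cavg of 10 or 100 ng/mL gives 1.5 or 15 µg/kg/day. Because the factor is constant, every summary statistic of Cavg converts in the same way, apart from the CVs, which stay as they are.
- Totals not planned: ESP15228, 16 women × 7 = 112 products; EZE-glucuronide, 8 × 7 = 56. Together that is 168 products, all within the SAP 17.4 calculation of amounts, leading to 16 + 8 = 24 subject totals.

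**What summary tables alone would give.** If the seven amounts were tabled with the same n at each collection, their means would add to the mean total. The SD of the total would not follow. With an equal SD s per collection and an assumed common correlation ρ, it is s × √(7 + 42ρ):

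| ρ (assumed) | SD of 24-hour total |
|---|---|
| 0 | 2.65 s |
| 0.5 | 5.29 s |
| 1 | 7.00 s |

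The median and range of the total would be lost as well. Subject listings fill this gap: SAP 17.4 lists all milk concentrations and parameters by subject. If amounts or volumes are listed too, each total is a sum of seven numbers. The SAP does not name them in that sentence, so this is likely but not certain.

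**Whether adding the totals is free.** SAP 8.4.2 excludes a below-limit concentration that precedes the last quantifiable one, and does not say what that collection contributes to a sum. The not-evaluable rule in SAP 17.4 covers only AUC24h and Cavg. A metabolite Σ(C × V) would therefore need a rule of its own.

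**The case for a change.** The strongest reply is that infant exposure to active drug includes active metabolites. If a metabolite reaches milk at ratio r to its parent (same mass units, r assumed), a parent-only total leaves out r/(1 + r) of the combined amount: 9% at r = 0.1, 50% at r = 1, 91% at r = 10. The raw quantities are measured anyway, six supportive rows would hold the result (2 parameters × 1 metabolite in Cohort 1, 2 × 2 in Cohort 2), and protocol 14.3.2.2 permits extra parameters. Naming them beforehand would also remove any suspicion of choosing after the fact.

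Part of this stands. The scope mismatch exists, the analytes are not named in the final summary list, and the extra rows would be a reasonable courtesy to readers.

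It does not show a defect. The documents give no value for r, so the omitted share may be negligible. A combined amount would need molecular weights and an additivity assumption that are not supplied. Metabolite Cavg is reported whatever the data show, so the per-kg exposure is visible to anyone who multiplies by 150. The totals that remain depend on how much each woman happened to pump. With a purely descriptive analysis and metabolite concentrations reported in full, there is little room for selective reporting. The same protocol section that permits extra parameters leaves the final list to the SAP, and the SAP has made its choice.

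**Conclusion.** No change is needed. The synopsis sentence is a clerical slip, contradicted by the primary endpoints in the same synopsis and overridden by the SAP. The unnamed analytes at the end of SAP 17.4 are a gap that any analyst fills from the definitions in SAP 17.3: BA in both cohorts and EZE in Cohort 2.

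Followed as written, the plan meets its parent-drug exposure objective and its metabolite concentration objective, and no primary estimate changes. The absent output is at most 24 subject totals, assuming complete collections in 8 women per cohort. The per-kg counterpart is one multiplication away, at 0.15 µg/kg/day per 1 ng/mL of Cavg. Reporting the totals is optional and would bring its own question about below-limit collections.

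This rests on the stated objectives being the right test of the plan and on metabolite Cavg being tabled and listed, as SAP 17.2 and 17.4 provide.
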